CA	Carbohydrate antigen	PPV	Positive predictive value	
cDNA	Complementary DNA	RNA	Ribonucleic acid	
CEA	Carcinoembryonic antigen	RT-PCR	Reverse transcription polymerase chain reaction	
CRC	Colorectal cancer	SN	Sensitivity	
DR	Detection rate	SP	Specificity	
GEE	Generalized estimating equation	TNM	Tumor node metastasis classification	
Hb	Hemoglobin	TNR	True negative rate	
Ig	Immunoglobulin	TPR	True positive rate	
NEG	Negative			

1. Introduction of the test

1.1 Title of the study

Prospective study of the fecal-based miR-92a test for screening colorectal cancer in a general risk population.

1.3 Aims of the trial

The project is to perform fecal-based miR-92a test and immunochemical fecal occult blood test (FIT) on people at average risk of colorectal cancer (CRC). The performance of FIT and miR-92a and their combination for CRC and advanced adenomas (AA) [advanced neoplasia (AN)] will be analyzed by using colonoscopy and/or pathological findings as the gold standard, and the performance indicators including sensitivity, specificity, predictive values, diagnostic accuracy, likelihood ratios and overall compliance rate will be evaluated, to form an early screening and prevention strategy for the population at average risk of CRC.

1.4 Study population

This is a prospective study of a population at average risk for CRC. 16,505 subjects aged from 30 to 75 will be enrolled in this prospective study based on inclusion and exclusion criteria, if they are fully informed about the study and sign the informed consent. The investigators will continue to monitor the progress of enrolment and the rate of positivity for miR-92a, after the start of the study to determine whether enrolment should be terminated early.

1.5 Project schedule

- The clinical trial protocol was initially submitted for ethical review in April 2021, and the ethical review was completed by the leading unit in May 2021;
- The filing and approval of human genetic resources were completed in June 2021, followed by the completion of ethical review by the participating medical institutions in June 2021;
- Starting from July 2021, the screening and enrollment of subjects began, followed by information entry, collection
 of fecal samples, laboratory testing of fecal samples, and colonoscopy;
- Colonoscopies were undergone starting from November 2021, for subjects who were required to undergo the procedure according to the study protocol design;
- The data analysis and general report of the clinical trial were completed by the end of December 2023.

2. Project introduction

2.1 Background

CRC is one of the top-ranked cancers in terms of incidence and mortality both in China and globally. According to GloboCan2020, CRC accounts for 1,148,515 new cases and 576,858 deaths globally, ranking as the fifth in terms of global incidence among the most common cancers and holds the fifth highest mortality rate worldwide [1]. According to the relevant statistics in China, the incidence and death rate of CRC ranked 5th among all malignant tumors in 2017, with 376,000 new cases and 191,000 deaths [2]. Colonoscopy is currently the main diagnostic tool for CRC, but the complexity of the examination process, the low compliance of the test and the low accuracy of the preliminaries limit the advantages of colonoscopies. For example, if the patient's bowel is not adequately prepared or if the early lesions are not clearly visible on microscopy, these lesions are more likely to be missed. Furthermore, the substantial population at risk for CRC, particularly due to advancing age, coupled with the concentration of CRC epidemiology in economically

developed regions, presents challenges for colonoscopy to emerge as the primary screening method for individuals at risk [3]. This is attributed to issues such as low compliance rates and prolonged appointment waiting times, especially in regions with high incidence rates of the disease. In addition to colonoscopy, FIT is a commonly used primary screening tool for people at risk of CRC. The test is based on the qualitative detection of human hemoglobin in fecal samples by immunocolloidal gold assay, which is relatively simple and inexpensive to perform. Nevertheless, the limitations of the testing technology and result interpretation principle only allow for the detection of blood in fecal samples. Consequently, there may be a lack of effective correlation between the test results and the detection of pre-cancerous and high-risk lesions, especially adenomas in their advanced stages of development. While other blood-based markers such as carcinoembryonic antigen (CEA) and carbohydrate antigen (CA) show significant clinical utility in diagnosing CRC and monitoring patients during the perioperative and postoperative phases [4, 5]. They may not offer superior specificity and early detection capabilities for AN. Up to now, CRC auxiliary diagnostic products based on molecular biology and technology have been marketed in China, including septin-9 methylation test based on blood samples and DNA methylation test based on fecal samples [6, 7]. The former does not have the advantage of early detection and has a significantly lower positive rate compared to fecal samples, whereas the latter's targets and technology are derived from the technology of marketed products in Europe and the United States and are based on basic research and clinical trials in European and American populations, with a lack of clinical data support in Asian populations, especially in China.

MiR-92a is a class of small molecule non-coding RNA, belonging to the miR-17-92 gene cluster on human chromosome 13, which promotes the proliferation and migration of CRC cells by inhibiting PTEN, KLF4, and downstream p21 gene [8-10], is a specific target for CRC, and has important value for early diagnosis, postoperative surveillance and prognosis of CRC [11]. Stool samples from patients with CRC or pre-cancerous high-risk lesions including polyps contained significantly higher levels of miR-92a than normal. Meanwhile, small RNAs can be effectively used as markers for CRC detection due to their stability and reproducibility in stool samples [12].

2.2 Fecal miR-92a detection technology

We has previously completed clinical trials in Shenzhen People's Hospital, Guangzhou Sun Yat-sen University Cancer Prevention and Treatment Centre and Tianjin People's Hospital for its miR-92a test based on stool samples. The product was approved for marketing by the National Medical Products Administration (NMPA) in March 2018 (National Machinery Registration Standard 20183400108) through the national innovative medical device special approval channel. A total of 1306 clinical subjects were enrolled in the pre-market clinical trial, including 340 cases of confirmed colorectal

cancer, 901 cases of confirmed non-colorectal cancer, including esophageal cancer, gastric cancer, hepatocellular cancer, pancreatic cancer, cholangiocarcinoma, oral cancer, gastritis, enteritis, appendicitis and peptic ulcer, 901 cases of patients with colorectal polyps and adenomas, as well as a control group of the normal population, and 65 cases of patients with post-surgery CRC.

The expression of miR-92a in the intestinal epithelial cells of CRC patients increases with the onset of the disease. Consequently, the detection of miR-92a in exfoliated intestinal epithelial cells obtained from fecal samples serves as an effective tool for identifying the risk of colorectal cancer (CRC), including pre-cancerous polyps, adenomas, and other related lesions. Stool miR-92a was detected by extracting total RNA from stool samples using a nucleic acid extraction reagent and performing miR-92a-specific RT-PCR reaction. The primers and probes in the reaction solution are designed to specifically bind to and amplify miR-92a and its reverse transcription product. Compared to colonoscopy, the fecal-based miR-92a assay demonstrates high sensitivity and specificity in detecting CRC and precancerous lesions like adenomas. It functions as a potent screening tool for identifying individuals at risk for CRC, and facilitates comprehensive screening and diagnosis of CRC and precancerous lesions, notably adenomas in their advanced stages.

2.3 Research content

The study was conducted at Shenzhen People's Hospital (SZH) (head unit), Shenzhen Bao'an District Hospital of Traditional Chinese Medicine (BAT) and Tianjin Nankai Hospital (NKH). 16,505 subjects were enrolled according to the inclusion and exclusion criteria. During the recruitment process, the researchers will fully introduce the content, risks and value of the study to the subjects. Subjects will sign an informed consent to participate in the study after they have been fully informed of the content, risks and benefits of the study and their questions have been answered. A short interview using the CRC risk questionnaire will be conducted and a stool sample collection kit will be given to the subjects. One stool sample will be collected according to the stool sample collection instructions and returned to the clinical site. The sample will be used for fecal-based miR-92a and FIT (9. Instructions for stool sample collection). Colonoscopy and/or pathology will be performed on subjects with positive fecal-based miR-92a and/or FIT. Some screen-negative individuals will also be randomly selected for colonoscopy and/or pathological examination. The study will analyze the performance of FIT, miR-92a and their combination in the screening of CRC and AA [advanced neoplasia (AN)] using colonoscopy and/or pathological findings as the gold standard.

3. Research target

To analyze the performance of FIT and fecal-based miR-92a and their combination for AN, and to evaluate the performance indicators and form an early screening and prevention strategy for people at average risk of CRC.

4. Research methods

4.1 Colorectal cancer risk questionnaire interview

After signing the informed consent, subjects will receive the CRC risk questionnaire. The content of the questionnaire will not be used as a basis or reference for the determination of the test results.

4.2 Fecal-based miR-92a test

4.2.1 Principle

The miRNA detection in fecal-based shedding of intestinal epithelial cells has good reproducibility and stability. MiR-92a is a molecular marker specific for CRC, and its level is elevated in CRC or precancerous lesions compared with that of normal subjects. MiR-92a can be used to evaluate the risk of CRC and precancerous lesions of the subjects through fecal samples.

4.2.2 Main components

Components	Number of tubes	Volume
MiR-92a RT-PCR solution	1	185 μΙ
MiR-92a PCR reaction solution	1	800 μl
MiR-92a RT-PCR primer	1	25 μl
MiR-92a PCR primers and probes	1	85 μΙ
Quality control product 1	1	20 μl
Quality control product 2	1	50 μl
Reverse transcriptase	1	33.5 μl
RNAase inhibitors	1	6.5 μl
Taq enzyme	1	15 μl
0.1% DEPC water	2	1200 μl

MiR-92a microRNA-92a, RT-PCR reverse transcription polymerase chain reaction, PCR polymerase chain reaction, RNAase ribonuclease, DEPC diethyl pyrocarbonate

4.2.3 Storage conditions and expiration dates

The kits are valid for 12 months when stored at -20 °C and below;

Try to avoid repeated freezing and thawing when using the kit, and the number of times of freezing and thawing

shall not exceed 5;

The date of manufacture and expiration are shown on product labels.

4.2.4 Procedure

Fecal-based miR-92a test uses nucleic acid extraction reagents to extract total RNA from stool samples and perform

miR-92a-specific RT-PCR on them.

The primers and probes in the reaction solution can bind to and amplify miR-92a and its reverse transcription

products.

During the amplification process, once the probe complements and binds to the reverse transcription cDNA strand

containing the miR-92a template, the fluorescent dye group positioned at the 5' end of the probe is cleaved by the

Taq-enzyme, resulting in the release of fluorescent signals.

The fluorescence signal released by the probe is monitored by a quantitative fluorescence PCR instrument in real

time and a curve is generated to reflect the miR-92a content in the sample.

Results determination:

a. Positive: The Ct value of the sample to be tested is < 32.00.

b. Negative: The Ct value of the sample to be tested is ≥ 32.00 .

4.3 Fecal occult blood test

4.3.1 Principle

A fecal occult blood test looks for human hemoglobin (Hb) in a stool sample. Hb is a common target for fecal occult

blood testing. Immunocolloidal gold-based fecal occult blood testing uses a monoclonal antibody to Hb as a double

antibody sandwich to detect human Hb in stool samples. The FIT in this trial is an immunochromatographic assay for the

detection of occult blood in fecal samples using two protein targets, hemoglobin and transferrin.

The Hb in the tested specimen first reacts with the gold standard anti-human hemoglobin monoclonal antibody A to

form a complex, which moves upward chromatographically along the membrane by capillary action, and when it reaches

6

the detection line, it binds with the anti-human hemoglobin monoclonal antibody B encapsulated in the detection zone to form a red line, which is a positive result, and if the detection zone does not have a red line, then it is a negative result.

4.3.2 Main components of the kit

[figure not shown]
The test cards and strips consist of a sample pad, a gold standard pad, a nitrocellulose membrane, an absorbent paper, and a PVC plate. The gold standard pad has anti-human hemoglobin monoclonal antibody A, the nitrocellulose membrane which coated with anti-human hemoglobin monoclonal antibody B, and the quality control line which coated with sheep anti-mouse IgG antibody. Additional information on the FIT kit is detailed in the table below.

4.3.3 Storage conditions and expiration dates

- Storage conditions: Store at 4 °C to 30 °C in a dry place, protected from light and heat; do not freeze; take precautions to avoid heat, freezing and thawing in summer and winter.
- Expiration dates: 18 months. The reagent should be used within 1 hour after opening the inner package (humidity: 20 90%, temperature: $10 50 \,^{\circ}\text{C}$).

4.3.4 Procedure

- Leave the reagent at room temperature for 30 min before use and return to room temperature (20 − 30 °C). Do not open the inner package until it is ready for use, and use it within 1 hour after opening the inner package (humidity: 20 − 90%, temperature: 10 − 50 °C).
- Add 1 ml of distilled won water to the fecal specimen and mix well for examination.
- Open the inner package, take out the reagent and put it on the countertop.
- Add 2 drops of diluted sample (approximately 80 ml) vertically to the reagent spiking tip and observe the result within 5 min, after which the result is invalid.
- Results determination:
 - a. Positive: A red line appears at each of the test line (T line) and control line (C line).
 - b. Negative: A red line appears at the C line only.
 - c. Invalid: The absence of a red line at the C line indicates an operational error or reagent failure.

4.4 Colonoscopy

Principle: Colonoscopy uses a fiberoptic endoscope inserted through the anus to view the rectum, sigmoid colon, descending colon, transverse colon, ascending colon and ileocecum during entry and exit. Colonoscopy allows visualization of intestinal lesions and the microscopic removal or tissue sampling of polyps, such as progressive adenomas, and the removal of foreign bodies from the colorectum.

Procedure: Subjects are instructed to orally consume 3000 – 4000 ml of polyethylene glycol on the evening before the examination. During the examination, the endoscopist adheres to standardized protocols to ensure a comprehensive and clear visual of the anal canal, rectum, sigmoid colon, descending colon, transverse colon, ascending colon and ileocecal region. After microscopic lancing, clamping or scraping of the lesion, the tissue removed by the colonoscope is examined according to standard histopathological methods to determine the nature of the lesion.

4.5 Screening experiment design

In parallel experiments, if either of the tests (T) yielded positive results, the overall outcome (R) was considered positive, as demonstrated in equation (1). Parallel testing can enhance sensitivity and lower false negative occurrences, though at the expense of reduced specificity.

$$R_{+} = T_{1+} U T_{2+} U \dots U T_{n+}$$
 (1)

$$SN(Tc) = \sum_{i=1}^{S} SN(Ti) + \prod_{i=1}^{S} SN(Ti) - (\sum_{i=1}^{S} SN(Ti))^{2} + \sum_{i=1}^{S} (SN(Ti))^{2}$$
 (2)

$$SP(Tc) = \prod_{i=1}^{S} SP(Ti)$$
(3)

When the number of tests S=2, the formula can be substituted as:

$$SN(Tc) = SN(T_1) + SN(T_2) - SN(T_1) \times SN(T_2)$$

$$= SN(T_1) + SN(T_2) \times [1 - SN(T_1)]$$
(4)

$$SP(Tc) = SP(T_1) \times SP(T_2)$$
(5)

5. Study population

5.1 Enrolment of subjects

The target population for this study was the average risk group for CRC aged 30 – 75 years. Subjects will be recruited based on the inclusion and exclusion criteria. Subjects will be excluded if they are recruited but meet the exclusion criteria. The target population is divided into age groups of 5 years. Laboratory testing will be initiated as soon as the subject has been successfully recruited and has provided a satisfactory stool sample. The researchers will monitor the progress of the subjects and the results of the laboratory tests in real time and will count the number of enrolments and fecal-based miR-92a positivity in time to determine whether to terminate the enrolment early.

5.2 Inclusion criteria

- Age between 30 and 75;
- Able to provide a stool sample and agree to undergo colonoscopy;
- Agree to participate in the study and sign an informed consent.

5.3 Exclusion criteria

- History of colorectal cancer or treatment with colorectal cancer drugs or surgery;
- History of advanced adenomas or colorectal polyps;
- Patients with severe mental retardation or speech communication disorder, severe heart, brain, lung disease or liver or kidney dysfunction;
- Patients with severe ulcerative colitis;
- Patients with hereditary CRC syndromes (e.g., Lynch syndrome, FAP);
- Subjects who request to withdraw from this study;
- Subjects who are deemed unsuitable for this study by the investigator after thorough discussion.

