6.1 Subjects enrolled

Subject enrolment will be initiated after the project has been approved by the ethical review committee. The researchers will determine whether to recruit subjects based on the inclusion and exclusion criteria, explain the study in detail to those who meet the enrolment criteria and are interested in participating in the trial, and answer all questions raised by the subjects to ensure that they are fully aware of the content of the study, the risks, benefits and other relevant information. The subject signs the informed consent to participate in the study. Subjects have the right to withdraw from the study at any stage after successful recruitment. Subjects may contact the study leader to inquire about test results or to request withdrawal.

The researcher will use the CRC risk questionnaire to interview the subjects after they have signed the informed consent to participate in the study. One copy of the informed consent will be retained by the subject after signing, and the other copy will be kept on file together with the subject's information and code. The subject code will be used as the unique identification number of the subject, which will be used to identify the samples, laboratory test data, and summarize the required information to meet the needs of information query and verification. Stool samples will be taken from the subjects.

11

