6.6.1 Subjects tested positive for fecal samples

The researchers actively followed up with positive subjects, i.e., fecal miR-92a positive subjects, FIT positive subjects, miR-92a + FIT positive subjects, and provided education on bowel health and CRC prevention while facilitating the timely completion of colonoscopy.

The researchers counted the results of fecal samples in batches and contacted the subjects with positive fecal miR-92a and/or FIT tests to follow up with them to receive the colonoscopy and to make an appointment for the colonoscopy. After confirming the subject's acceptance of the colonoscopy and setting a date for the colonoscopy, the researcher contacted the subject again to follow up with him/her to learn about the colonoscopy precautions and to remind him/her to pick up the medications and materials needed for the bowel preparation. The researcher retrieved the colonoscopy report and pathology results in a timely manner after the subject completed the colonoscopy.

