- After clicking on the model to execute the function, drop down the cell and generate random data.
- Select the data cells in column B, right-click the mouse and select "Sort" in the "ascending".
- By expanding the selected region, the data in column A can be redistributed randomly.
- Select the first three rows of the worksheet, select the toolbar in the "data" menu in the "combination" option, read
 the number obtained that is randomly selected subjects.
- Initiate a follow-up telephone call with three randomly selected subjects to follow up on the completion of the colonoscopy. If any of the subjects refused to undergo colonoscopy, the randomized follow-up subjects were deferred.

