7.1.3 Endpoint

The objective of the study is to analyze the performance of FIT, miR-92a and their combination for the detection of AN, evaluating performance indicators such as sensitivity, specificity, predictive values, diagnostic accuracy, likelihood ratios, and overall compliance rate, to formulate a strategy for early screening and prevention of CRC for an average-risk population. Once the project is initiated, the researchers will monitor the progress of enrolment, results of miR-92a and FIT, and colonoscopy and pathology results in real time, and will determine whether to terminate enrolment early based on the number of enrolments and fecal-based miR-92a positivity rate.

Data summaries for all subjects will be summarized in a frequency table:

	Colonoscopy	and/or histopatholog	T. 4-1	
Test result	CRC	AA	NEG	Total
Positive	a	b	c	a+b+c
Negative	d	e	f	d + e + f
Total	a + d	b + e	c + f	N

CRC colorectal cancer, AA advanced adenomas, NEG negative (including polyps, other non-colorectal cancerous lesion and no findings)

- (1) The sensitivity and specificity will be calculated as:
- xx test sensitivity for subjects with CRC = a/(a + d)
- xx test sensitivity for subjects with AA = b/(b + e)
- xx test sensitivity for subjects with AN = (a + b)/(d + e)
- xx test specificity for subjects with negative findings = f/(c + f)
- (2) The PPV and NPV will be calculated as:
- PPV (CRC) = Probability of having CRC given a positive xx test result = a/(a + b + c)
- PPV (AA) = Probability of having AA given a positive xx test result = b/(a + b + c)
- PPV (AN) = Probability of having AN given a positive xx test result = (a + b)/(a + b + c)
- NPV = Probability of having negative findings on colonoscopy given a negative xx test result = f/(d + e + f)
- (3) The LRs will be calculated as:
- PLR (CRC) = P (Test positive | CRC)/P (test positive | No CRC) = a/(b+c)
- PLR (AA) = P (Test positive | AA)/P (test positive | No AA) = b/(a + c)
- PLR (AN) = P (Test positive | AA or CRC)/P (test positive | No AA nor CRC) = (a + b)/c
- NLR (NEG) = P (Test negative | NEG)/P (test negative | AA or CRC) = f/(d + e)

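### Section 5.3 makes a request to withdraw an exclusion criterion that also applies after recruitment, so test-positive subjects who formally withdraw can leave the compliance and positivity counts despite valid stool results

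*Protocol*

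**What the plan says.** Three statements have to be read together.

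- Protocol 5.3 (Exclusion criteria) includes "Subjects who request to withdraw from this study".
- Protocol 5.1 (Enrolment of subjects) states: "Subjects will be excluded if they are recruited but meet the exclusion criteria". It sets no time limit and does not restrict this to criteria assessable at baseline.
- Protocol 6.1 (Subjects enrolled) states: "Subjects have the right to withdraw from the study at any stage after successful recruitment".

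Colonoscopy is requested only once stool results are known. Under 6.6.1 the researchers "contacted the subjects with positive fecal miR-92a and/or FIT tests to follow up with them to receive the colonoscopy". Under 6.6.2 only randomly drawn negatives are called, and 8.1.3 offers undrawn negatives no free colonoscopy. Willingness is an entry condition in 5.2 ("Able to provide a stool sample and agree to undergo colonoscopy"), but the only rule for a later refusal concerns the drawn negatives in 6.6.2: "If any of the subjects refused to undergo colonoscopy, the randomized follow-up subjects were deferred". There is no matching rule for positives.

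The overall compliance rate is among the indicators in 1.3 ("likelihood ratios and overall compliance rate will be evaluated") and 7.1.3 ("likelihood ratios, and overall compliance rate"). Section 7.3 adds the detection rate of advanced neoplasia, and 7.4 compares DR and PR between the tests. No denominator is given for compliance or detection rate.

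**The concern.** A request to withdraw is something a subject does after joining. It is not a characteristic that makes the subject ineligible. Treating it as ineligibility turns a post-result event into a ground for exclusion, as if the subject should never have been enrolled, even when valid miR-92a and FIT results exist.

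The exclusion is also linked to the index test. Every subject positive on either test is called for an invasive examination; among negatives, only a sample is. The event most likely to prompt a withdrawal therefore falls on all positives and few negatives.

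If these subjects leave the counts, compliance loses people who were called and not examined, positivity loses positives from numerator and denominator, and the detection rate per subject keeps its numerator while its denominator shrinks.

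**Working it through.** **The plan's own figure.** Section 5.5 sizes the study on CRC sensitivity: 1.96² × 0.9 × 0.1 / 0.09² = 42.684, and 42.684 / 0.003 = 14,228, as stated. This N serves only as the base for the illustration.

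**Inputs.** From 5.5: CRC prevalence 0.3%, AA prevalence 3%, miR-92a sensitivity 90% (CRC) and 80% (AA), specificity 90%. Assumed, because the protocol gives no figure: the share d of positives who decline colonoscopy, 20% to 40%, and the share f of decliners who formally ask to withdraw, 10%, 50% or 100%.

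**Positivity with everyone kept.** p = 0.003 × 0.9 + 0.03 × 0.8 + 0.967 × 0.1 = 0.1234, which is 1,756 of 14,228.

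**Formulas.** The share of positives excluded is w = d × f.

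- Compliance as read = (1 − d) / (1 − w); true compliance = 1 − d.
- Positivity as read = (1 − w)p / (1 − wp).
- Detection-rate ratio = 1 / (1 − wp), since decliners contribute no detected lesion.

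| d | f | w | Positives excluded | True compliance | Compliance read | Positivity read | Detection-rate ratio |
|---|---|---|---|---|---|---|---|
| 20% | 10% | 0.02 | 35 | 80% | 81.6% | 12.1% | 1.002 |
| 40% | 10% | 0.04 | 70 | 60% | 62.5% | 11.9% | 1.005 |
| 20% | 50% | 0.10 | 176 | 80% | 88.9% | 11.2% | 1.012 |
| 40% | 50% | 0.20 | 351 | 60% | 75% | 10.1% | 1.025 |
| 20% | 100% | 0.20 | 351 | 80% | 100% | 10.1% | 1.025 |
| 40% | 100% | 0.40 | 702 | 60% | 100% | 7.8% | 1.052 |

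The last two rows are the extreme in which every decliner asks to withdraw.

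**A simplification.** The table ignores withdrawals among drawn negatives. If as many of them withdrew as positives, positivity at w = 0.20 would read 0.8 × 0.1234 / (1 − 2 × 0.2 × 0.1234) = 10.4% instead of 10.1%. That offsets little, and compliance among positives is untouched.

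**Accuracy measures.** Sensitivity, specificity and PPV in 7.1 need a colonoscopy result. A positive who leaves before colonoscopy is absent from those tables with or without this rule.

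**The case against.** - **Declining is not withdrawing.** This stands. The 5.3 criterion needs a request to withdraw. A positive who declines or does not attend, without asking to leave, is not excluded by it. A reader might infer that all colonoscopy refusers disappear and that compliance approaches 100% by construction. The text does not support that: it holds only if every decliner also formally withdraws, and nothing in the design forces this.
- **Section 5.1 may mean only people recruited in error, since 5.4 handles later removals.** This reading is possible. But a request to withdraw can hardly be met as a criterion before recruitment, and 5.4 does not list withdrawal.
- **Excluded need not mean dropped from every denominator, and an analysis plan that is not shown could define the denominators.** Fair as to missing definitions, which are not the point here. The point is that the protocol classes a post-result event as ineligibility. No section keeps these subjects in any denominator, and a plan that did so would have to depart from 5.1 and 5.3.
- **The stopping decision for enrolment is not shown to be affected.** This stands. Since 5.1 and 7.1.3 use miR-92a positivity to decide on early termination, a reader might infer that this decision is biased. But positivity is monitored in real time from laboratory results, no section says the count is revised after withdrawals, and no threshold is given.
- **The terms are undefined.** PR in 7.4 is not in the visible abbreviation list, and overall compliance rate has no definition. Reading them as positivity rate and colonoscopy uptake is natural but remains an assumption. No bias in the paired comparison of the two tests has been calculated.
- **The gap between enrolled and included.** A reader might take 16,505 − 15,586 = 919 as evidence of such exclusions. Section 5.5 links the margin to unqualified samples and gives no breakdown, so it shows nothing about withdrawals.

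**Conclusion.** The point holds in a limited form. As written, 5.1, 5.3 and 6.1 class a tested, recruited subject who formally withdraws as excluded, and the colonoscopy call makes this more likely for positives than for negatives. Compliance and positivity are the measures exposed, on the assumptions that overall compliance rate means colonoscopy uptake, that PR means positivity rate, and that exclusion removes the subject from the count.

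The size depends mainly on how many decliners formally withdraw, which the protocol does not give. With one in ten doing so, the distortion is 1.6 to 2.5 percentage points of compliance and 0.2 to 0.4 points of positivity. With half, it is 8.9 to 15 points and 1.1 to 2.2 points. The detection rate is inflated by at most 2.5% to 5.2% in relative terms, and only if all decliners withdraw. The principal accuracy results are unaffected by this rule. The document does not show that any such exclusion was made. This is a misstated rule that should be corrected, not a threat to the main analysis.

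**What to change.** - Delete the withdrawal item from 5.3 and align 5.1, so that post-recruitment exclusion refers to conditions present at entry.
- Treat withdrawal as a post-enrolment disposition. Keep every subject with a valid stool result in the positivity, detection-rate and compliance denominators, unless consent to use of the data is also withdrawn.
- In 7.1.3, define compliance as colonoscopies completed divided by all subjects positive on either test.
- Report withdrawals and colonoscopy refusals separately, by miR-92a and FIT result.

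The cost is a few lines of wording and one disposition table. Compliance and detection rates will look less favourable wherever withdrawn subjects would otherwise have been dropped. Section 1.5 describes the analysis as completed by the end of 2023, so the table would now have to come from recorded data, within the limits of each subject's consent.
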